3.1.1.1. Part 1 Intravenous (IV) Administration

In Part 1, PF-06863135 will initially be studied as an IV formulation in sequential dose levels (0.1, 0.3, 1, 3, 10, 30, 50 μ g/kg or higher if indicated) in adult patients with relapsed/refractory multiple myeloma, who have received a proteasome inhibitor, an immunomodulatory drug (IMiD) and an anti CD38 monoclonal antibody (mAb) where approved and available either in combination or as a single agent. Additional dose levels (lower, intermediate or higher) may be evaluated. If toxicity is observed at the starting dose level of 0.1 μ g/kg, 0.03 μ g/kg will be evaluated. Subsequent to the starting dose level, if dose de-escalation is recommended by the mTPI model after DLT evaluation, intermediate dose levels between the previous dose and current dose may be studied. Depending on the observed safety and tolerability profile of PF-06863135, dose levels above 50 μ g/kg or higher if indicated may be explored. All patients will also be monitored from Day 22 to Day 60 for late toxicities (see [Section 3.2.1](#)).

If within 21 days after the initial infusion a dose level induces symptoms consistent with \geq Grade 3 CRS and lasts for >24 hours despite standard of care treatment for the management of CRS per the guidelines of the institution, Investigator, or treating physician, and it is considered not to be due to an IRR, allergic reaction, anaphylaxis or other causes, evaluation of Part 1 SC or Part 1.1 IV Maintenance administration may be initiated.

3.1.1.2. Part 1 Subcutaneous (SC) Administration

Part 1 SC administration has been triggered based on the emerging clinical and PK data from IV cohorts at 80 μ g/kg, one dose level higher ("Dose IV +1") than the tested IV dose level of 50 μ g/kg in Part 1 IV administration that is deemed safe and has not experienced a Grade 3 CRS event.

Depending on the observed safety and tolerability profile of PF-06863135, each dose level for SC administration will be increased by a maximum of 3-fold.

Depending on evaluation of immunogenicity, safety, efficacy, PK and/or PD data the SC administration portion may be placed on hold or discontinued and Part 1.1 Priming and Maintenance Dose Escalation administration may be re-initiated if appropriate.

PF-06863135
 C1071001
Final Protocol Amendment 9, 28 March 2023

3.1.1.3. Part 1.1 Priming and Maintenance Cohorts

Part 1.1 is an alternative dosing regimen that will be initiated only if a priming dose for IV or SC has been declared in Part 1. The decision to evaluate a regimen that includes a priming dose may be made by the investigators and sponsor prior to reaching an MTD/MAD using the following criteria as guidance:

- If a dose level induces symptoms consistent \geq Grade 3 CRS lasting for >24 hours (despite treatment with standard of care per the institution's, Investigator's, or treating physician's guidelines for the management of CRS) considered not to be due to an infusion related reaction (IRR), allergic reaction, anaphylaxis or other causes, then a lower dose, which has been evaluated in at least 2-4 patients, will be chosen as a priming dose (Dose Prime) for subsequent cohorts.
- If a Dose Prime is selected, dose escalation will continue to determine the MTD/MAD of a dose regimen that includes a priming dose.
- If a dose level induces confirmed CRS of Grade 4 considered not to be due to an IRR, allergic reaction, anaphylaxis or other causes, then a lower dose, which has been evaluated in at least 2-4 patients, will be chosen as a priming dose (Dose Prime) for subsequent cohorts.
- In addition, observation of a confirmed CRS event that meets the above qualifications following later infusions (ie, after Cycle 1 Day 1) or CRS events that are approaching the limit of tolerability may prompt the investigators and sponsor to include evaluation of a Dose Prime for subsequent cohorts.

After confirmation of the safety of Dose Prime, the treatment schedule will implement the inclusion of the fixed priming dose as the first dose (C0D1) followed by a maintenance dose 1 week later (C1D1) that will continue to be escalated in subsequent cohorts following an mTPI method. The starting maintenance dose level will be no greater than 2-fold above the priming dose (see [Section 3.1.4](#)). Depending on the observed safety and tolerability profile of PF-06863135, each maintenance dose level administration will be increased by a maximum of 2-fold. After the MTD/MAD has been established, the priming dose may potentially be further verified in connection to the established MTD/MAD/RP2D, including consideration of more than one priming step, if indicated, using information from all patients who were included in the initial priming dose determination as well as those enrolled in subsequent dosing cohorts.

SCHEDULE OF ACTIVITIES B: WITH PRIMING DOSE AND SCHEDULE OF PHARMACOKINETIC, SOLUBLE FACTOR AND CYTOKINE ACTIVITIES B will then be utilized in Part 1.1. In Part 1.1, patients will receive the priming dose on C0D1 during the priming dose portion of Cycle 0. The priming dose will remain the same for all dose level cohorts. The maintenance dose will be administered one week later on C1D1 and for subsequent cycles.

PF-06863135

C1071001

Final Protocol Amendment 9, 28 March 2023

To closely manage acute toxicities, all patients receiving a priming dose will be hospitalized for at least 24 hrs on both C0D1, and C1D1. The hospitalization period may be extended if the patient experiences abnormal laboratory findings or ongoing adverse events that require further hospitalization.

For safety reasons, a staggered start will be employed at each dose level; the first patient will be dosed, and observed for 48 hours. The 48 hr observation period for the first patient in each dose level in Part 1.1 will begin on C1D1 during the second hospitalization period. If no safety concerns arise during this 48 hr period from start of treatment, then subsequent patients will be enrolled into the same maintenance dose level.

Decisions for maintenance dose escalation will be made based on toxicities observed within the DLT observation period (Cycles 0 and 1). Subsequent to starting the maintenance dose level, if dose de-escalation is recommended by the mTPI model after evaluation, intermediate dose levels between the previous dose and current dose may be studied. At least 6, up to approximately 16 patients must be enrolled into a maintenance dose level that is determined to be the maximum tolerated dose (MTD)/MAD.

Once a dose level has been declared safe, patients at lower dose levels who have completed 60 day late toxicity observation period may escalate to the next higher dose level, if criteria outlined in [Section 3.1.4.1 Criteria for Intrapatient Dose Escalation](#) have been met.

Additional intra-patient maintenance dose escalations will also be permitted after a minimal interval of 60 days from first administration of maintenance dose.

Alternative strategies for increasing dosing such as a step-up regimen or prophylactic steroids may also be considered and implemented to further improve tolerability if needed.

3.1.1.4. Part 1 Combination Dose Finding

Parts 1C, 1D and 1E, are dose finding safety cohorts for PF-06863135 in combination with lenalidomide, pomalidomide or dexamethasone, respectively. Upon determining the PF-06863135 RP2D/MTD/MAD and route of administration as monotherapy either with or without priming dose in Part 1, Parts 1C, 1D and 1E will be initiated to study the safety of PF-06863135 in combination with lenalidomide, pomalidomide, or dexamethasone. Parts 1C and 1D will be started with PF-06863135 one dose level below the MTD/MAD and escalated one dose level unless the RP2D is below the MTD/MAD in which case the RP2D will be used as the starting dose of PF-06863135. If in Parts 1C, or 1D, the combination is not well tolerated, doses of PF-06863135 may be de-escalated to a lower dose level below the starting dose of PF-06863135 used in combination. Part 1E will be a combination of PF-06863135 at RP2D/MTD/MAD and dexamethasone. If this combination is not well tolerated, Part 2E may not be initiated.

As described in [Section 3.4](#), a dose of 1000 µg/kg SC weekly has been selected as the RP2D for PF-06863135 as a single agent. This single agent RP2D will be administered as a fixed dose of 76 mg (a fixed dose equivalent of 1000 µg/kg; see [Section 1.2.9.4](#) for rationale) following a priming dose of 44 mg (a fixed dose equivalent of 600 µg/kg) administered one week earlier. Similarly, Part 1 combination dose finding (Part 1C and Part 1D) will be

PF-06863135
C1071001
Final Protocol Amendment 9, 28 March 2023

administered as fixed doses for PF-06863135 with maintenance doses started one week after the priming dose; the starting dose is one dose level below the single agent RP2D as described in Table 1:

Table 1. Table of Potential Fixed Dose Levels

| Dose level ^a | Priming Dose (mg) | Maintenace Dose (mg) |
|-------------------------|-------------------|----------------------|
| 0 | 24 | 32 |
| 1 (starting) | 32 | 44 |
| 2 ^b | 44 | 76 |

a. Dose level refers to designated dose levels for Part 1C and Part 1D

b. Designated dose level for Part 1E

Part 1C will investigate PF-06863135 in combination with lenalidomide in sequentially escalating doses of PF-06863135. This safety cohort will start with the dose level MTD-1/MAD-1 or RP2D (whichever is lower) of PF-06863135 from the Part 1 dose escalation and 15 mg dose of lenalidomide in order to select the combination RP2D. If the combination regimen is not well tolerated, a dose that is lower than the RP2D determined for single-agent PF-06863135 may be evaluated in combination before proceeding to Part 2. If necessary, de-escalation will be guided by an mTPI design. PF-06863135 will be administered on C1D1 and weekly or every 2 weeks or once per cycle (CXD1) thereafter with or without a priming dose. A dose of 15 mg of lenalidomide will be administered orally on Days 1-21. PF-06863135 and lenalidomide will be administered over a cycle of 28 days. A staggered enrollment strategy will be applied at each dose level: when a dose level opens for enrollment, the first patient will be dosed, and observed for 96 hours beyond C1D1. If no safety concerns arise during this 96 hr period from C1D1 of PF-06863135 and lenalidomide, subsequent patients will be enrolled into the same dose level. To closely manage acute toxicities, patients will be hospitalized on C1D1. It is expected that Part 1C will enroll approximately 9-16 patients.

Part 1D will investigate PF-06863135 in combination with pomalidomide in de-escalation doses. This safety cohort will evaluate the MTD-1/MAD-1 or RP2D dose level (whichever is lower) of PF-06863135 from Part 1 dose escalation and a standard of care dose of pomalidomide in order to select the combination RP2D. If the combination regimen is not well tolerated, a dose that is lower than the RP2D determined for single-agent PF-06863135 may be evaluated in combination before proceeding to Part 2. If necessary, de-escalation will be guided by mTPI. The first dose of PF-06863135 will be administered on C1D1 and weekly thereafter. A dose of 4 mg of pomalidomide will be administered orally on Days 1-21. PF-06863135 and pomalidomide will be administered over a cycle of 28 days. A staggered enrollment strategy will be applied at each dose level: when a dose level opens for enrollment, the first patient will be dosed, and observed for 96 hours. If no safety concerns arise during this 96 hr period from C1D1 of PF-06863135 and pomalidomide, subsequent patients will be enrolled into the same dose level. To closely manage acute toxicities,

PF-06863135
 C1071001
Final Protocol Amendment 9, 28 March 2023

patients will be hospitalized on C1D1. It is expected that Part 1D will enroll approximately 9-16 patients.

Part 1E will investigate PF-06863135 in combination with dexamethasone. This safety cohort will evaluate the RP2D fixed dose level of PF-06863135 monotherapy and a fixed dose of dexamethasone, at a dose of 40 mg. For subjects older than 75 years or underweight (body mass index [BMI] <18.5), dexamethasone premedication may be given prior to PF-06863135 at a dose of 20 mg. If the combination regimen is not well tolerated due to PF-06863135, PF-06863135 may be de-escalated in combination according to modified toxicity probability interval (mTPI) design. Each cycle of the combination of PF-06863135 and dexamethasone starting with Cycle 1 will be 28 days. If the combination regimen is not well tolerated as guided by mTPI, Part 2E may not be initiated. Dexamethasone would begin on C0D1 and it will be dosed as premedication prior to PF-06863135 administration. If a patient has received dexamethasone for 6 months or PF-06863135 is discontinued, then dexamethasone should be discontinued unless clinical rationale to continue dexamethasone is provided by investigator and approved by sponsor. Patients who need to discontinue treatment with dexamethasone may continue to receive treatment with PF-06863135. If a dose of PF-06863135 is held or skipped, then dexamethasone should not be administered until PF-06863135 is restarted. It is expected that Part 1E will enroll approximately 9-16 patients.

3.1.2. Part 2 Dose Expansion

Part 2 dose expansion phase will be divided into 4 cohorts as follows: Part 2A (PF-06863135 as monotherapy), Part 2C (PF-06863135 in combination with lenalidomide), Part 2D (PF-06863135 in combination with pomalidomide), and Part 2E (PF-06863135 in combination with dexamethasone) which will evaluate safety and anti-myeloma activity of PF-06863135 at the monotherapy/combination RP2D.

Based on emerging clinical data from the Part 1 dose escalation, either IV or SC administration including priming and maintenance dose Q1W or Q2W will be selected for the Part 2 dose expansion.

If the SC administration is selected for Part 2 dose expansion, all patients in 2C, 2D and 2E will receive a subcutaneous fixed dose of PF-06863135 at the Q1W RP2D (with or without a priming dose given at C0D1 1 week prior to C1D1). Part 2A patients will also receive a subcutaneous fixed dose of PF-06863135 at either the RP2D Q1W or Q2W schedule, depending on emerging clinical data in Part 1.

For lenalidomide, Part 2C, 15 mg orally (PO) will be administered daily on days 1–21 of a 28 day cycle starting C1D1 in combination with the MTD/MAD or RP2D of PF-06863135 determined in Part 1C (with or without a priming dose of PF-06863135 given at C0D1, 1 week prior to C1D1).

For pomalidomide, Part 2D, 4 mg PO will be administered daily on days 1–21 of a 28-day cycle starting C1D1 in combination with the MTD/MAD or RP2D of PF-06863135 determined in Part 1D (with or without a priming dose of PF-06863135 given at C0D1 1 week prior to C1D1).

PF-06863135

C1071001

Final Protocol Amendment 9, 28 March 2023

For dexamethasone, Part 2E, 40 mg PO will be administered as premedication 60 ± 30 minutes prior to PF-06863135 starting C0D1 in combination with the MTD/MAD/RP2D fixed dose of PF-06863135 determined in Part 1. For subjects older than 75 years or underweight (body mass index [BMI] <18.5), dexamethasone premedication may be given 60 ± 30 minutes prior to PF-06863135 at a dose of 20 mg.

The RP2D selected will be based on the MTD or the MAD, and further evaluation of other covariates such as disease burden, soluble plasma BCMA level, and body size information will also be utilized. Selection of 1 hr or 2 hr intravenous administration (if utilized in Part 2) will be based on the incidence of IRRs. Approximately 80 patients may be enrolled into Part 2 (see [Section 9.3 Sample Size Determination](#)) with approximately 20 patients in Parts 2A, 2C, 2D, and 2E. Patients from the dose finding combination cohorts of Parts 1C, and 1D treated at the dose levels selected for Part 2 may be counted towards sample size of the corresponding cohorts of Part 2.

Preliminary data from the Part 2 dose expansion may provide guidance in the Sponsor's decision to adjust the sample size of each arm, to add other available treatment combinations in a future amendment, or to initiate additional clinical studies.

3.1.3. Starting Dose

The starting dose for Part 1 IV administration will be 0.1 μ g/kg given weekly in 3 week cycles.

3.1.4. Criteria for Dose Escalation/De-Escalation

The study has been designed to establish the MTD/MAD defined as the dose that yields approximately 25% probability of DLT and considers equivalent doses that yield probability of DLT in the interval (Equivalence Interval) 20% to 30%.

All dose escalation/de-escalations will be guided by the mTPI design and therefore 2-4 patients will be enrolled in each cohort (see [Section 3.1 Study Overview](#)).

The potential dose levels to be evaluated for Part 1 IV administration are listed in [Table 2](#). The potential dose levels to be evaluated for Part 1 SC administration are listed in [Table 3](#).

Dose escalation for Part 1 IV and SC will start at dose level 1 for each ([Table 2](#) and [Table 3](#)).

In Part 1, for both IV and SC administration, the maximum dose increase will be approximately 3 fold if no DLTs are observed; per mTPI, intermediate or higher doses may be evaluated based on clinical findings.

PF-06863135
C1071001
Final Protocol Amendment 9, 28 March 2023

Table 2. Table of Potential Dose Levels in Part 1 IV Administration

| Dose level | Dose (μ g/kg) |
|------------|-----------------------|
| 1 | 0.1 |
| 2 | 0.3 |
| 3 | 1.0 |
| 4 | 3.0 |
| 5 | 10.0 |
| 6 | 30.0 |
| 7 | 50.0 |

Table 3. Table of Potential Dose Levels in Part 1 SC Administration

| Dose level | Dose (μ g/kg) |
|------------|-----------------------|
| 0 | 50 |
| 1 | 80 |
| 2 | 130 |
| 3 | 215 |
| 4 | 360 |
| 5 | 600 |
| 6 | 1000 |

In Part 1.1, the starting maintenance dose will be no more than 2-fold above the priming dose established from Part 1. Maximum maintenance dose increases will be 2-fold (100%).

Q2W dosing would be evaluated upon reaching MTD/MAD. Cycles for Q2W dosing would be 4 weeks rather than the 3 weeks with Q1W dosing. Both Q1W and Q2W dosing may be considered for Part 2A expansion from Part 1.

Once the first DLT is observed, the maximum increase would increase no more than 2-fold up to 3 μ g/kg, and no more than 67% beyond 3 μ g/kg.

Parts 1C, and 1D will combine escalating doses of PF-06863135 starting at the monotherapy MTD-1/MAD-1 or RP2D (whichever is lower) dose level and increasing to the monotherapy RP2D/MTD, if applicable, in combination with a standard dose of lenalidomide or pomalidomide, respectively. De-escalation of PF-06863135 to a lower dose level may occur if necessary.

In Part 1E, the cohort that includes dexamethasone will evaluate PF-06863135 at a priming dose of 44 mg followed by a maintenance dose of 76 mg administered. De-escalation of PF-06863135 to a lower dose level may occur if necessary.

PF-06863135

C1071001

Final Protocol Amendment 9, 28 March 2023

The mTPI method relies upon a statistical probability algorithm, calculated using all patients treated in prior and current cohorts at the same dose level to determine (Decision Rules) where future cohorts should involve dose escalation, no change in dose, or dose de-escalation as presented in Table 4 (see also [Section 9.2 Statistical Methods and Properties and Appendix 8](#)).

Table 4. Decision Rules

| Number of Patients Having DLT | Number of Patients Treated at a Dose Level | | | | | | | | | | |
|-------------------------------|--|-----|-----|-----|-----|-----|-----|-----|------|------|------|
| | n=2 | n=3 | n=4 | n=5 | n=6 | n=7 | n=8 | n=9 | n=10 | n=11 | n=12 |
| 0 | E | E | E | E | E | E | E | E | E | E | E |
| 1 | S | S | S | E | E | E | E | E | E | E | E |
| 2 | U | D | D | S | S | S | S | S | S | S | E |
| 3 | | U | U | U | D | S | S | S | S | S | S |
| 4 | | | U | U | U | U | D | S | S | S | S |
| 5 | | | | U | U | U | U | U | U | D | S |
| 6 | | | | | U | U | U | U | U | U | U |

D: De-escalate the dose; E: Escalate the dose; S: Stay at the dose; U: Unacceptable toxicity

Note: If one patient has a DLT event observed in a dose cohort with 2 patients enrolled, additional patients may be enrolled for dose escalation assessment. Any DLT observed accounts for decision rules.

Dose escalation will stop under any of the following conditions:

- The maximum sample size has been achieved;
- Approximately 6-16 patients have been enrolled at a dose that is predicted to be the MTD/MAD;
- All doses explored appear to be overly toxic and the MTD/MAD cannot be determined.

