3.1.1. Part 1 Monotherapy Dose Escalation and Part 1.1 Priming and Maintenance Cohorts

SCHEDULE OF ACTIVITIES A and **SCHEDULE OF PHARMACOKINETIC, SOLUBLE FACTOR AND CYTOKINE activities A** will be utilized in Part 1.

To closely manage acute toxicities, all patients enrolled into Part 1 dose escalation phase will be hospitalized on C1D1 (Also for at least 24 hrs if a priming dose is given on C0D1). The hospitalization period may be extended if the patient experiences abnormal laboratory findings or ongoing adverse events that require further hospitalization. The need for mandatory hospitalization as well as its length will be re-assessed for patients enrolled in Parts 2A, 2C, and 2D based on safety data from Part 1 after agreement of sponsor and investigators at the time of monotherapy MTD/MAD/ and RP2D determination

For safety reasons, a staggered enrollment strategy will be applied for Parts 1 and 1.1 at each dose level; the first patient will be dosed and observed for 48 hours. If no safety concerns arise during this 48 hr period from start of treatment, then subsequent patients will be enrolled into the same dose level. All patients in Part 1 and Part 1.1 will be monitored closely for dose limiting toxicities (DLTs, see [Section 3.2](#)). Decisions for dose escalation will be made based on DLTs observed within the DLT observation period. A modified toxicity probability interval (mTPI) method, targeting a DLT rate of 25% and an acceptable equivalence interval of 20%-30% will be utilized for dose escalation Part 1 (see [Section 3.1.4](#)). At least 6, up to 16 patients must be enrolled into a dose level that is determined to be MTD/MAD. Upon reaching MTD/MAD, up to approximately 6-12 patients total at selected level(s) below the MTD/MAD weekly and Q2W dosing up to the same dose intensity as the MTD/MAD weekly regimen may be evaluated further to support the RP2D decision.

Assessment of late toxicities will also be completed after the DLT observation period to 60 days after C1D1 for all patients. Once a dose level has been declared safe, patients at lower dose levels who have completed the 60 day late toxicity observation period may escalate to the next higher dose level, if criteria outlined in [Section 3.1.4.1](#) Criteria for Intrapatient Dose Escalation have been met. Additional intra-patient dose escalations will

PF-06863135

C1071001

Final Protocol Amendment 9, 28 March 2023

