3.1.4.1. Criteria for Intrapatient Dose Escalation

Intrapatient dose escalation to the next dose-level will be permitted in this study for patients in dose escalation phase. Data gathered from patients following intra-patient dose escalation will be excluded from MTD/MAD evaluation. Intrapatient dose-escalation to the next dose level is permitted if all of the following conditions are met. Further intrapatient dose escalations are permitted, and will be based on the same criteria for each escalation.

1. The next dose level is safe after DLT observation in all patients for a minimum of 60 days;
2. The candidate for intra-patient dose-escalation tolerated the current dose level well, with highest drug-related toxicity observed being Grade 2 or below;
3. A bone marrow aspirate and disease staging lab tests can be performed within 1 week before start of treatment with the escalated dose (a bone marrow aspirate is mandatory unless the investigator assesses that there is an unjustifiable risk for it

PF-06863135

C1071001

Final Protocol Amendment 9, 28 March 2023

and/or the patient refuses to undergo a bone marrow procedure; if a bone marrow aspirate or biopsy was performed within the past 28 days prior to planned start of escalated dose, only disease staging lab tests must be performed);

4. A discussion between the investigator and sponsor has been completed, and it is agreed that this will be in the patient's best interest.

A patient whose dose has been escalated will not contribute to the assessment of the number of DLTs at the escalated dose level.

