3.2. Dose Limiting Toxicity (DLT) Definition

Monitoring for DLTs will occur during Part 1. Severity of adverse events (AEs) will be graded according to National Cancer Institute Common Terminology Criteria for Adverse Events (CTCAE) version 4.03. The severity of cytokine release syndrome (CRS) will be assessed according to the grading described by Lee et al. (2014 and 2019,^{2,3} See [Appendix 5](#)). For the purpose of dose escalation, the DLT observation period will be up to the end of Cycle 1 in each patient. For those patients receiving a priming dose, Cycle 0 and Cycle 1 would be included in the DLT observation period. DLT evaluable patients will include patients that have experienced a DLT in the DLT observation period or. DLT evaluable patients will also include those who received all of their planned doses of PF-06863135 in the initial DLT observation period if Q2W dosing is being evaluated or at least all but one of their planned doses of PF-0686135 if Q1W dosing is being evaluated, provided a dose was not missed due to toxicity attributed to study drug. Safety information from any patients that do not meet DLT evaluable criteria could still be considered for overall dose escalation decisions although they would not factor into mTPI decision rules.

Any of the following adverse events observed within the DLT observation period considered related to PF-06863135 or PF-06863135 in combination with lenalidomide, pomalidomide, dexamethasone, will be classified as DLTs:

Hematological:

- Grade 4 neutropenia lasting >5 days. Except in lenalidomide combination cohort where it can be managed by dose reduction of lenalidomide in the next cycle.
- Febrile neutropenia (defined as an absolute neutrophil count [ANC] <1000/mm³ with a single temperature of >38.3°C [101°F], or a sustained temperature of ≥38°C [100.4°F] for more than one hour). If fever is determined to be a symptom of CRS confirmed by clinical course and cytokine levels and resolves in a manner consistent with CRS, this would no longer be considered a DLT, and the patient may resume treatment.
- Grade ≥3 neutropenia with infection.
- Grade 4 thrombocytopenia (unless the study entry baseline count was ≥25,000 and <50,000 to take into account bone marrow suppression due to multiple myeloma, in

PF-06863135

C1071001

Final Protocol Amendment 9, 28 March 2023

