9.2.2. Statistical Method for Estimating the MTD/MAD

As previously described, the estimated MTD is the highest tested dose level with DLT rate ≤ 0.30 in at least 6 DLT-evaluable patients (ie, per protocol analysis set). It is assumed that higher doses result in higher toxicity rates. But, due to the relatively low number of patients that may be potentially allocated to any dose, this assumption may be violated.

To estimate the MTD/MAD the study will continue accruing until one of the three stopping conditions below is triggered:

1. The maximum sample size has been achieved.
2. MTD/MAD has been identified with sufficient accuracy: 6 to 16 patients have been accumulated on a dose that is currently estimated to be the MTD/MAD; or
3. All doses explored appear to be overly toxic and the MTD/MAD cannot be determined.

Clinical judgment will be exercised in taking forward doses to the expansion cohort(s), in case no clear choice exists between more than 1 competing MTD/MAD. This decision will be based upon the combination of data related to safety, anti-tumor activity, and clinical judgment of the investigators and the sponsor.

PF-06863135
C1071001
Final Protocol Amendment 9, 28 March 2023

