Appendix 8. DETAILED DOSE ESCALATION/DE-ESCALATION SCHEME FOR mTPI DESIGN

| Number of Patients Having DLT | Number of Patients Treated at a Dose Level | | | | | | | | | | |
|-------------------------------|--|-----|-----|-----|-----|-----|-----|-----|------|------|------|
| | n=2 | n=3 | n=4 | n=5 | n=6 | n=7 | n=8 | n=9 | n=10 | n=11 | n=12 |
| 0 | E | E | E | E | E | E | E | E | E | E | E |
| 1 | S | S | S | E | E | E | E | E | E | E | E |
| 2 | U | D | D | S | S | S | S | S | S | S | E |
| 3 | | U | U | U | D | S | S | S | S | S | S |
| 4 | | | U | U | U | U | D | S | S | S | S |
| 5 | | | | U | U | U | U | U | U | D | S |
| 6 | | | | | U | U | U | U | U | U | U |

E = Escalate to the next higher dose

S = Stay at the current dose

D = De-escalate to a lower dose

U = The dose is Unacceptably toxic

MTD/MAD = The highest dose yields the probability of DLT within the equivalence interval (20%, 30%).

Escalation/De-escalation algorithms for total number of patients treated at the current dose level (current and previous cohorts):

- With 1 patient treated at current dose level:
 - 0 DLT -> escalate;
 - 1 DLT or other toxicities occur (ie, those that have the potential to be DLTs if more severe) -> may add additional patients to assess safety on a cohort size of n=2-4.
- With 2 patients treated at current dose level:
 - 0 DLT -> escalate;
 - 1 DLT -> remain at the same dose;
 - 2 DLTs -> de-escalate and consider current dose as intolerable.
- With 3 patients treated at current dose level:
 - 0 DLT -> escalate;
 - 1 DLT -> remain at the same dose;
 - 2 DLTs -> de-escalate;

PF-06863135

C1071001

Final Protocol Amendment 9, 28 March 2023

- 3 DLTs -> de-escalate and consider current dose as intolerable.
- With 4 patients treated at current dose level:
 - 0 DLT -> escalate;
 - 1 DLTs -> remain at the same dose;
 - 2 DLTs -> de-escalate;
 - 3-4 DLTs -> de-escalate and consider current dose as intolerable.
- With 5 patients treated at current dose level:
 - 0 or 1 DLT -> escalate;
 - 2 DLTs -> remain at the same dose;
 - 3-5 DLTs -> de-escalate and consider current dose as intolerable.
- With 6 patients treated at current dose level:
 - 0-1 DLT -> escalate;
 - 2 DLTs -> remain at the same dose;
 - 3 DLTs -> de-escalate;
 - 4-6 DLTs -> de-escalate and consider current dose as intolerable.
- With 7 patients treated at current dose level:
 - 0-1 DLT -> escalate;
 - 2-3 DLTs -> remain at the same dose;

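### The mTPI decision table is indexed by patients treated, while Section 3.2 keeps patients who are not DLT-evaluable out of the mTPI rules; where the two counts differ, the treated count is the less cautious one

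*Protocol*

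**What the plan says.** **Passages that count patients treated.** Protocol 3.1.4 describes the algorithm as "calculated using all patients treated in prior and current cohorts at the same dose level to determine (Decision Rules"). The column header of Table 4 is "Number of Patients Treated at a Dose Level". Appendix 8 introduces its cell-by-cell rules as "Escalation/De-escalation algorithms for total number of patients treated at the current dose level (current and previous cohorts").

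**Passages that count DLT-evaluable patients.** Protocol 3.2 lets safety data from non-evaluable patients inform the overall dose decision, "although they would not factor into mTPI decision rules". SAP Section 5 (DLT Evaluable Set) and SAP 6.2.1 repeat that rule. Protocol 9.2.2 estimates the MTD from the DLT rate "in at least 6 DLT-evaluable patients (ie, per protocol analysis set"). The worked example in 3.3 and the sample size in 9.3 also refer to evaluable patients.

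**The minimum at the MTD.** Section 3.1.1 states it by enrollment: "At least 6, up to 16 patients must be enrolled into a dose level that is determined to be MTD/MAD". Section 9.2.2 states it in evaluable patients.

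**The SAP.** Its Section 2 says that it supersedes the protocol's statistical considerations. Its decision table (Table 1) prints columns n=2 to 12 without saying what n counts. SAP Section 5 lists both the DLT Evaluable Set and the Safety Analysis Set for the DLT analysis, and SAP 8.2.1 bases the primary analysis on the Safety Analysis Set.

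**The concern.** One decision table has two possible denominators, and they do not differ symmetrically. Section 3.2 states that "DLT evaluable patients will include patients that have experienced a DLT in the DLT observation period", so anyone classed as non-evaluable has no DLT in the window. Counting that person as treated raises n and leaves the DLT count where it was.

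The group is not a neutral one. Under 3.2 it includes patients who missed a dose because of drug toxicity that fell short of a DLT. On the treated count they enter as event-free observations.

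The Part 1 primary endpoint is the number of DLTs, and escalation decisions follow from that number over n. If the SAP's Safety Analysis Set is used for DLT rates, the same dilution carries into the reported rates.

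**Working it through.** **Inputs (Protocol 9.2.1).** Target DLT rate 0.25; e1 = e2 = 0.05, giving a proper-dosing interval of 0.20 to 0.30; Beta(0.5, 0.5) prior; exclusion threshold 0.95.

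**Step 1: reproduce Table 4.** With x DLTs in n patients the posterior is Beta(0.5 + x, 0.5 + n − x). The unit probability mass (UPM) of an interval is its posterior probability divided by its length: 0.20 for underdosing, 0.10 for proper dosing, 0.70 for overdosing. The largest UPM gives E, S or D. U applies if P(rate > 0.25) exceeds 0.95. All 67 filled cells match the printed table.

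**Step 2: add one DLT-free patient.** Hold x fixed and move from n to n + 1. The 67 cells less the 7 in the n=12 column leave 60 steps.

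- More cautious: 0
- Unchanged: 50
- Less cautious: 10

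| DLTs | Change in n | Change in decision |
|---|---|---|
| 1 | 4 to 5 | S to E |
| 2 | 2 to 3 | U to D |
| 2 | 4 to 5 | D to S |
| 2 | 11 to 12 | S to E |
| 3 | 5 to 6 | U to D |
| 3 | 6 to 7 | D to S |
| 4 | 7 to 8 | U to D |
| 4 | 8 to 9 | D to S |
| 5 | 10 to 11 | U to D |
| 5 | 11 to 12 | D to S |

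Two such patients change 14 cells and three change 17, again all less cautious.

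**Step 3: one step in full.**

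- 1 DLT in 4, Beta(1.5, 3.5): UPMs are 0.3553/0.20 = 1.777 (under), 0.1976/0.10 = 1.976 (proper) and 0.4471/0.70 = 0.639 (over). The decision is Stay.
- 1 DLT in 5, Beta(1.5, 4.5): UPMs are 0.4507/0.20 = 2.253, 0.2120/0.10 = 2.120 and 0.3373/0.70 = 0.482. The decision is Escalate.

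**Step 4: illustration, on an assumption.** Suppose 4 evaluable patients and 1 non-evaluable patient; the documents do not give such a split. On the evaluable count (n=4) escalation needs 0 DLTs among the 4. On the treated count (n=5) it needs 0 or 1. With true DLT rate p:

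- P(escalate), evaluable count = (1 − p)^4
- P(escalate), treated count = (1 − p)^4 + 4p(1 − p)^3

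| True rate | Evaluable count | Treated count |
|---|---|---|
| 25% | 0.316 | 0.316 + 0.422 = 0.738 |
| 30% | 0.240 | 0.652 |
| 35% | 0.179 | 0.179 + 0.384 = 0.563 |
| 40% | 0.130 | 0.475 |

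At 35%, the probability of De-escalate or Unacceptable is P(2 or more DLTs in 4) = 0.437 on the evaluable count and P(3 or more in 4) = 0.126 on the treated count.

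**The case against.** The best defence is that the documents, read together, already choose evaluable patients. Section 3.2 is the specific rule, it names the mTPI, and the SAP repeats it twice. Sections 3.3, 9.2.2 and 9.3 count evaluable patients, and 9.1 allows replacement. On that reading, treated in Table 4 is loose shorthand. This has force, and it shows which way to repair the text. It does not remove the conflict: no passage says that the table's n is the evaluable count, and the SAP leaves n undefined and points the primary analysis to everyone dosed.

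Other objections also stand in part:

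- **Most steps do not move.** Fifty of 60 are unchanged, the zero-DLT row is always Escalate, and only two of the ten changes end in Escalate. The illustration uses 4 to 5, one of those two.
- **The direction has exceptions.** Section 3.2.1 lets late toxicities enter the mTPI, so a non-evaluable patient could add an event. The per-protocol set in 9.1, which 9.2.2 equates with evaluable, drops major treatment deviations with no exception for a patient who had a DLT.
- **Evaluable is not one thing.** SAP 6.2.1 also lists at least one dose as adequate dosing for Part 1 without priming. Under that criterion, treated and evaluable coincide there and the dilution vanishes.
- **The MTD is partly protected.** Section 3.3 bars a dose with DLT incidence above 30%, and 9.2.2 uses evaluable patients.
- **The two minimums of 6 can both be met.** One describes accrual and the other estimation. Even so, six enrolled does not guarantee six evaluable.

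A reader might also infer that the treated count takes in patients who escalated into a dose level from a lower one. The documents settle this: Section 3.1.4 limits the count to prior and current cohorts, SAP 5.1 places patients by initial dose, and Section 3.1.4.1 says "A patient whose dose has been escalated will not contribute to the assessment of the number of DLTs at the escalated dose level".

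**Conclusion.** The inconsistency is real, and the text should be corrected. Section 3.1.4, Table 4 and Appendix 8 use patients treated; Section 3.2 and its SAP counterparts exclude non-evaluable patients from the same rules. Under the Section 3.2 definition, and apart from late toxicities, the treated count never gives a more cautious decision. For one such patient it gives a less cautious decision in 10 of 60 steps.

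A reader might infer that the trial escalated too readily or that its MTD/MAD is wrong. The documents do not support that. They give neither the number of non-evaluable patients nor the denominator used at any past decision, so the actual effect may be nil. The probabilities above rest on an assumed split of 4 plus 1 and on assumed true rates. Enrollment is complete and the monotherapy RP2D has been selected, so what remains at stake is how past decisions and DLT rates are documented and reported.

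**What to change.** 1. Settle one definition of DLT-evaluable. Reconcile Section 3.2, the per-protocol set in 9.1 that 9.2.2 cites, and the differing criteria within SAP 6.2.1.
2. In Section 3.1.4, the Table 4 header, Appendix 8 and SAP Table 1, define n as DLT-evaluable patients under that definition.
3. State the minimum of 6 at the MTD in DLT-evaluable patients wherever it is given by enrollment, as 9.2.2 already does.
4. In SAP 8.2.1, base DLT rates on the DLT Evaluable Set. Adverse event summaries can stay on the Safety Analysis Set.
5. In the clinical study report, give patients treated, patients evaluable and DLTs for each dose level, and state which denominator was used for each past escalation decision.

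The cost is wording in two documents and one table in the report. No patient, visit or new data collection is needed.
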